3.5.1.2 Wound closure at 12 weeks post-treatment

The number and percentage of patients with a wound closure at 12 weeks post-treatment will be presented with a 95% CI. This will be derived as any wounds that closed on or prior to the 12 week visit in the EDC.

3.5.1.3 Time to wound closure

Time to wound closure will be summarized by mean, median, standard deviation, quartiles, minimum and maximum. Additionally, the distribution of the time to wound closure will be analyzed by KM methodology. Any wound that was not closed will be censored at the last date on study. The 25th percentile, median and the 75th percentile will be presented along with the 95% CIs using the methodology of Brookmeyer and Crowley (1982)² using the log-log standard error. KM rates will be presented for each week with the corresponding 95% CIs using the log-log transformation methodology of Kalbfleisch and Prentice (1980)³. Plots of the KM curve will also be provided.

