### 10.3 Primary Efficacy Analyses

---

The three primary endpoints are:

- Rate of epithelial migration (mm/week) by perimeter
- Wound closure at 12 weeks post-treatment
- Time to wound closure

Summary statistics with 95% CI will be provided for all primary endpoints. The Clopper-Pearson method will be used for binary proportions (wound closure at 12 weeks post-treatment).

Additionally, distribution of time to wound closure will be estimated using the Kaplan Meier (KM) method and the 25th percentile, median, and 75th percentile will be presented along with 95% CIs.

The primary endpoint, rate of epithelial migration, will be evaluated for skewness using the Kolmogorov Smirnov test. In the event of significant skewness, the interquartile range will be reported in addition to the 95% CI.

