1.3 Study endpoints

The primary endpoints of the study are:

- Rate of epithelial migration (mm/week) measured by wound perimeter on photograph
- Wound closure at 12 weeks (± 1 wk) post-treatment
- Time from initial treatment with Varithena® to wound closure

The secondary endpoints of the study are:

- Percent of wounds remaining closed at 3 months (± 1 wk) post-wound closure date, non-healed wounds are not included in percent calculation
- For healed wounds, rate of VLU recurrence (at same site)
- Change in pain on NPRS compared to baseline at 12 weeks (± 1 wk), 6 months (± 1 wk), 12 months (± 1 wk) post-treatment
- Change on Euroqol five dimension five level questionnaire (EQ-5D-5L) quality of life assessment compared to baseline at 12 weeks (± 1 wk) and 12 months (± 1 wk) post-treatment
- Change in Venous Clinical Severity Score (VCSS) from baseline to 12 week (± 1 wk) and 12 month (± 1 wk) follow-up
- Number of ulcer-free weeks defined as weeks from time of closure (complete epithelialization is recorded) to date of recurrence (at same site) or last contact if no recurrence (at study completion or withdrawal)

2 Changes to protocol analysis

The interim analyses were expanded to look at hospitalization and safety information. Please see section 3.8 for further details.

Additional exploratory analyses from the Wound Health Index (WHI) will not be conducted.

NPRS analyses will use data from both the sDCT and the electronic data capture (EDC). The analysis will be summarized by each week through 12 weeks, 6 months and 12 months post-treatment. Additionally, the categories by severity will not be summarized but rather the numerical scale will be summarized and presented in a shift table. Refer to section 3.5.2 for further details.

Sub-group analyses will not be performed. There is not enough data collected for the analyses to be meaningful.

3 Statistical methods and analysis

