3.1 General methodology and definitions

Continuous data will be summarized with means, medians, standard deviations, quartiles (25th and 75th), minima and maxima, unless otherwise specified. Categorical data will be summarized with observed counts and percentages for each category; 95% confidence interval (CI) will be calculated using the Clopper-Pearson (1934)¹ or exact method for binary proportions. For time to event variables, the number of patients, number of events, the median and 95% CI of the median, and quartiles will be provided by the Kaplan Meier (KM) method.

Baseline is defined as the last available measurement taken before the first treatment.

Follow up wound image assessments will need to be slotted into the appropriate visit window described in the table below. Days relative to date of first treatment will be calculated as:

$$\text{Days} = \text{Date of assessment} - \text{Date of treatment} + 1$$

Visit Timepoint	Target Day	Days Relative to Date of Treatment
1 Week	7	≤ 7
2 Weeks	14	8 to ≤ 14
3 Weeks	21	15 to ≤ 21
4 Weeks	28	22 to ≤ 28
5 Weeks	35	29 to ≤ 35
6 Weeks	42	36 to ≤ 42
7 Weeks	49	43 to ≤ 49
8 Weeks	56	50 to ≤ 56
9 Weeks	63	57 to ≤ 63
10 Weeks	70	64 to ≤ 70
11 Weeks	77	71 to ≤ 77
12 Weeks	84 to 91	77 to ≤ 98
6 Month	183	153 to 213
12 Month	365	335 to 395

If any assessment has more than one wound image in the visit timepoint, the worst (largest) value will be used in the analysis. The range in the target day for weeks were used to mark all follow-up visit timepoints appropriately in instances where the sites could have used either weeks or months for the follow-up. Any assessments outside of the window will not be summarized.

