3.5.2.6 Number of ulcer free weeks (time to recurrence)

The number of ulcer free weeks (time between healed wound and recurrence) will be summarized by mean, median, standard deviation, quartiles, minimum and maximum. If a patient's wound healed but did not have a recurrence, the patient will be censored at the last date of study. Additionally, the distribution of the time to recurrence will be analyzed by KM methodology. The 25th percentile, median and the 75th percentile will be presented along with the 95% CIs using the methodology of Brookmeyer and Crowley (1982)² using the log-log standard error. KM rates will be presented for each week through 12 weeks with the corresponding 95% CIs using the log-log transformation methodology of Kalbfleisch and Prentice (1980)³. Plots of the KM curve will also be provided.

Information for recurrence will be based on data from the EDC.

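### SAP 3.5.1.3 adds a raw mean, SD, median and quartiles to the Kaplan-Meier results for time to wound closure, a right-censored primary endpoint, without saying how unclosed wounds enter

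*SAP*

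**What the plan says.** SAP 1.3 lists among the primary endpoints "Time from initial treatment with Varithena® to wound closure". SAP 3.5.1.3 opens its analysis with "Time to wound closure will be summarized by mean, median, standard deviation, quartiles, minimum and maximum". KM comes next, as an addition: "Additionally, the distribution of the time to wound closure will be analyzed by KM methodology". For wounds still open, the rule is: "Any wound that was not closed will be censored at the last date on study". From KM, a further set of quantiles is then promised: "The 25th percentile, median and the 75th percentile will be presented along with the 95% CIs". A median and quartiles are therefore planned twice. The section does not say whether the raw set covers closed wounds only or all wounds, nor which median is the reported result.

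The SAP's general rule in 3.1 is that, for time-to-event variables, "the median and 95% CI of the median, and quartiles will be provided by the Kaplan Meier (KM) method". Protocol 10.1 has the same rule. Protocol 10.3 adds "Summary statistics with 95% CI will be provided for all primary endpoints" and then asks for KM quartiles for this endpoint; SAP 3.5.1 repeats both requests.

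SAP 3.5.2.6 has the same construction for a secondary endpoint: "The number of ulcer free weeks (time between healed wound and recurrence) will be summarized by mean, median, standard deviation", followed by KM. SAP 1.3 and protocol 5.4, however, define ulcer-free weeks as running to recurrence or, without recurrence, to last contact.

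**The concern.** A raw mean or median needs one number per wound, and an unclosed wound has no closure time. There are two ways to get one.

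- **Closed wounds only.** This selects on the outcome. The slowest wounds are dropped, so the summary is too short whenever wounds are censored (except in the trivial case where all of them left before the first closure).
- **All wounds, with the censoring time used as the closure time.** This is too short once patients leave before 12 months. SAP 3.3.1 provides for that: withdrawal, loss to follow-up, death and a sponsor stop are listed as reasons for discontinuation.

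Some censoring is likely. Eligible ulcers are at least 3 months old, and wounds expected to close within 12 weeks without additional treatment are excluded (protocol 6.2). The registry is single-arm with no hypothesis test (SAP 1.1.1), so the descriptive figures are its result. Two medians for one primary endpoint, with the shorter one unlabelled, invite quotation of the wrong one.

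**Working it through.** The plan states no closure rate, dropout rate or expected median, so there is no figure of its own to reproduce. The check asks how far apart the two planned summaries would be.

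**Inputs**
- Follow-up T = 52 weeks (SAP 1.1: about 12 months).
- Proportion closed by T: h = 0.69, 0.88 or 0.93. These are borrowed from the background studies in protocol 4.1: 69% after at least 6 months, 88% at one year, 93% at 48 months. Using them as 52-week values here is an assumption.
- Exponential closure times (assumption).
- Dropout by week 52: d = 0 first, then 15%, exponential and independent of healing (assumption).

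**Formulas, no dropout**
- Closure rate λ = −ln(1 − h)/T
- KM median = ln 2/λ
- Closers-only median = −ln(1 − h/2)/λ
- Closers-only mean = 1/λ − T(1 − h)/h
- Restricted mean to week 52 = h/λ

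Worked for h = 0.69: λ = 1.1712/52 = 0.02252 per week. KM median = 0.6931/0.02252 = 30.8. Closers-only median = −ln(0.655)/0.02252 = 0.4231/0.02252 = 18.8. Closers-only mean = 44.4 − 52 × 0.31/0.69 = 21.0. Restricted mean = 0.69 × 44.4 = 30.6.

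| Closed by week 52 | λ | KM median | Closers-only median | Shortfall | Restricted mean | Closers-only mean |
|---|---|---|---|---|---|---|
| 69% | 0.02252 | 30.8 | 18.8 | 39% | 30.6 | 21.0 |
| 88% | 0.04077 | 17.0 | 14.2 | 16% | 21.6 | 17.4 |
| 93% | 0.05114 | 13.6 | 12.2 | 10% | 18.2 | 15.6 |

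At 69% closure the KM upper quartile is not reached within 52 weeks. The closers-only upper quartile is −ln(1 − 0.75 × 0.69)/0.02252 = 32.4 weeks.

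**All wounds, no dropout.** Every unclosed wound takes the value 52. The raw median is then the KM median (for example 17.0 weeks at 88%), provided at least half the wounds close, and the raw mean is the 52-week restricted mean. The upper quartile can still mislead: at 69% closure it would be printed as 52 weeks, where KM reports it as not reached.

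**All wounds, 15% dropout.** The dropout rate is δ = −ln(0.85)/52 = 0.003125. The raw median is ln 2/(λ + δ), and the raw mean is [1 − (1 − h)(1 − d)]/(λ + δ). KM and the restricted mean still target the values in the table.
- 69%: median 0.6931/0.02565 = 27.0 against 30.8; mean 0.7365/0.02565 = 28.7 against 30.6.
- 88%: median 0.6931/0.04390 = 15.8 against 17.0; mean 0.898/0.04390 = 20.5 against 21.6.
- 93%: median 0.6931/0.05426 = 12.8 against 13.6; mean 0.9405/0.05426 = 17.3 against 18.2.

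**Sensitivity.** Over simulated scenarios with 50% to 93% closure, 0% to 30% dropout, and exponential or Weibull (shape 1.5) times, the closers-only median was below KM by about 7% (93% closure, shape 1.5, no dropout) to about 63% (50% closure, 30% dropout, exponential).

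**The case against.** The case against is substantial, and much of it stands.

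- **A valid analysis is already planned.** SAP 3.5.1.3 gives a censoring rule, KM quartiles with intervals, weekly KM rates and curves. A reader might infer that the primary endpoint has no sound estimate. The documents do not support that; the defect lies in the added raw summary.
- **The protocol asks for summary statistics on every primary endpoint.** Removing them outright would depart from protocol 10.3. The request can be met with a summary suited to censored data.
- **The table mock-ups are in a separate document (SAP 1).** They may name the analysis set. Even so, the SAP text departs from its own section 3.1 and should settle the point.
- **Conflict with KM is not inevitable.** With all wounds included and no early exit, the medians agree. The raw SD is distorted by truncation, but it is not simply too short.
- **Larger gaps are tempting but unsupported.** The 142 days in protocol 4.1 is a mean time to healing, so it cannot stand in for a median of about 20 weeks. A model with a fixed share of wounds that never close would give a much larger gap, but the documents supply no such share. The mean should be compared with the 52-week restricted mean, because a 12-month registry cannot estimate an unlimited mean.
- **Ulcer-free weeks differ.** As defined, to recurrence or last contact, they are fully observed, and protocol 10.4 asks for both summaries. A raw mean of that quantity is legitimate, and any shortening would make the result look worse. The objection reaches 3.5.2.6 only where the quantity is called time to recurrence.

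What remains is that an unlabelled raw summary of a censored primary endpoint, with an unstated analysis set, sits beside KM and against the SAP's general rule.

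**Conclusion.** The point holds, as a change that should be made and not as a fatal flaw. The direction is clear: a closers-only summary is too short whenever wounds are censored, and an all-wounds summary is too short once patients leave early. The size is conditional. With exponential closure, 52 weeks and no dropout, the closers-only median falls short of KM by 10% at 93% closure, 16% at 88% and 39% at 69%. Those closure proportions come from other studies with different follow-up, and the registry documents give neither a closure nor a dropout rate, so the figures are a range and not a forecast. KM and the restricted mean themselves assume that leaving the registry is unrelated to healing. No test or decision rule depends on the raw figures; what is at stake is which healing time is reported.

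**What to change.** 1. In SAP 3.5.1.3, report the median and quartiles of time to closure from KM only, as SAP 3.1 already says.
2. Meet the protocol's request for a summary statistic with a 95% CI by giving the restricted mean time to closure to week 52, with its interval.
3. If a raw summary is kept, label it 'among wounds that closed', show its n, and keep it out of the primary endpoint result.
4. In SAP 3.5.2.6, keep the raw summary only as observed ulcer-free weeks (to recurrence or last contact). Take the time-to-recurrence median and quartiles from KM only.

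The cost is a small change to SAP wording and table shells; no new data are needed. The reported healing time may look longer than the raw summary would have shown.

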## 6.3 Subject Completion

---

A subject is considered to have successfully finished the registry upon completion of the 12 month follow-up phone call.

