## 6.4 Withdrawal

---

For cases in which the subject does not complete all assessments and follow-up visits, the subjects are classified as follows:

- Investigator withdrawal – Investigator can withdraw a subject from the registry for a safety concern, non-compliance, or for any other concern warranting withdrawal of the subject in the judgment of Investigator. Reason for Investigator withdrawal of a subject and last date of contact for the registry are documented on the Completion Log.
- Subject withdrawal – Subjects may withdraw from participation at any time during the registry. All data collected prior to withdrawal shall remain part of the registry data. Reasonable effort should be made to encourage the subject to remain in the registry. If the subject declines, determine and document the reason for withdrawal on the Completion Log.
- Lost to follow-up – A subject is considered lost to follow-up if there have been at least three documented attempts to contact the subject for follow-up without success. Last date of contact is documented on the Completion Log.

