#### **8.1.4 Week 2 through Wound Closure (at WCC)**

---

The subject does not return to the investigational site at this time. The subject presents to a WCC for wound care and dressing changes on about a weekly basis. During each visit to the WCC, subject is asked to take a photograph (multiple photographs for circumferential wounds) of the wound and answer the NPRS question using the sDCT. It is important that the subject understands that the WCC staff may not be aware of the registry, so collection of the photograph(s) and answering the NPRS question should be completed independently. The subject should refer questions about the sDCT and data collection to the investigational site, or contact Tissue Analytics® for technical support.

If the wound is not healed at the Week 12 Follow-up visit, subject continues to collect photograph(s) and answer NPRS questions at weekly WCC visits until wound closure.

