#### **8.1.7 6 Months (±1wk) Post-Treatment (Telephone)**

---

Investigator or delegate contacts the subject by phone to perform the following:

- Assessment for VLU recurrence
- Assessment of medical compression therapy compliance
- Request that subject collects the following using the sDCT:
  - Photograph of wound area, or wound if reoccurred
  - NPRS
- EQ-5D-5L quality of life assessment (only collected at 12 Months)

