3.3 Disposition, Demographics, Baseline

3.3.1 Disposition

Patient disposition will be summarized for all patients. The following categories will be summarized:

- Number of patients screened
- Number and percentage of patients in the efficacy population
- Number and percentage of bilateral patients (2 target wounds)
- Number and percentage of patients who discontinued
- Reasons for discontinuation
 - Withdrawn
 - Lost to follow-up
 - Death
 - Study discontinued by sponsor
 - Other
- Duration on study (months)
 - Duration (months) = (earlier date of study exit/death – date of first treatment + 1)/30.4375

Reasons for discontinuation and study exit dates are collected outside of the EDC. The reasons will be mapped into the categories above by clinical and provided to statistical programming for inclusion in summary table.

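### Unclosed wounds are censored at an undefined last date on study, which can fall after the wound was last documented open, so time to closure can be biased toward later or lower closure

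*SAP*

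**What the plan says.** SAP 3.5.1.3 summarises time to closure and adds that "the distribution of the time to wound closure will be analyzed by KM methodology", with quartiles, weekly rates and plots. The censoring rule is one sentence: "Any wound that was not closed will be censored at the last date on study". The date is not defined there. Protocol 10.3 also specifies Kaplan-Meier but gives no censoring rule, and SAP 3.5.1.4 says only that nothing is imputed.

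The nearest candidates for the date are these:

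- **Study exit or death** (SAP 3.3.1, used for duration on study). The same section notes: "Reasons for discontinuation and study exit dates are collected outside of the EDC".
- **Last contact**, for patients lost to follow-up (Protocol 6.4): "A subject is considered lost to follow-up if there have been at least three documented attempts to contact the subject for follow-up without success", followed by "Last date of contact is documented on the Completion Log".
- **The 12-month contact**, for completers (Protocol 6.3): "A subject is considered to have successfully finished the registry upon completion of the 12 month follow-up phone call". Protocol 8.1.8 makes Month 12 a clinic visit with a photograph. The two sections need to be reconciled.

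None of these is defined as a date on which the wound was assessed.

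**The concern.** Kaplan-Meier needs a closure to be recordable for as long as the patient is counted at risk. Here observation of the wound and presence on study can separate.

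- From Week 2 until closure, Protocol 8.1.4 says: "The subject does not return to the investigational site at this time". Wound status comes from photographs the patient takes at a wound care center whose staff are not delegated by the site (Protocol 7.1.3).
- SAP 4.3 then removes images that are unreviewed or not evaluable.
- The site is scheduled to see the patient around Week 1, at Week 12 and at Month 12 (Protocol 7.1.4).
- The call 3 months after closure is triggered only once healing is known (Protocol 8.1.6).
- The 6-month call lists "Assessment for VLU recurrence", compression, a photograph and pain. It has no item asking whether a wound still open at Week 12 has since closed.

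For example, a patient who stops photographs at Week 14, answers the 6-month call at about Week 26 and is then lost would be carried as open for about 26 - 14 = 12 unobserved weeks.

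The same times feed the weekly rates, the quartiles and the Cox models in SAP 3.6. In the Cox models, a factor linked to lapsing could look like a factor linked to slow healing. The separate 12-week closure proportion (SAP 3.5.1.2) does not use the censoring date.

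**Working it through.** **No planned figure to reproduce.** The documents give no closure rate, lapse rate, gap length or sample-size calculation (SAP 1.1.1). Every input below is an assumption, and lapse is taken to be independent of healing.

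**Step 1: a case that can be checked by hand.** Assume 50% closure at Week 12 with a constant hazard, so F(t) = 1 - 2^(-t/12). This gives F(12) = 0.500, F(26) = 0.777 and F(52) = 0.950. Assume 20% of patients stop assessments at a week L spread evenly over Weeks 1 to 12, no later closure is recorded, and they stay on study to Week 52.

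- Average F(L) over L = 1,...,12 is 0.299, so 0.20 × (1 - 0.299) = 14.0% of all patients are carried as open without being observed.
- Nobody is censored before Week 52, so the Kaplan-Meier estimate under the SAP rule equals the proportion recorded closed, 0.80 F(t) + 0.20 × 0.299.
- Week 12: 0.400 + 0.060 = 0.460, against a true 0.500.
- Week 26: 0.622 + 0.060 = 0.682, against 0.777.
- Week 52: 0.760 + 0.060 = 0.820, against 0.950.

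Simulation with 200,000 patients gives 46.1%, 68.3% and 81.8%, in agreement. This is an outer case, because a Month 12 clinic visit would normally reveal the wound's status.

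**Step 2: vary the gap** (50% closure at Week 12, 20% lapse, no later closure recorded). Cells show Kaplan-Meier closure under the SAP rule / censoring when last seen open.

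| Lapse in weeks | Gap | Week 12 | Week 26 | Week 52 |
|---|---|---|---|---|
| 0-12 | none | 49.9 / 49.9 | 77.7 / 77.7 | 94.8 / 94.8 |
| 0-12 | 8 weeks | 46.4 / 50.0 | 75.0 / 77.8 | 94.1 / 94.7 |
| 0-12 | to Week 52 | 46.1 / 50.1 | 68.3 / 77.9 | 81.8 / 94.7 |
| 12-26 | 8 weeks | 49.9 / 49.9 | 75.9 / 77.7 | 94.0 / 94.7 |
| 12-26 | to Week 52 | 49.8 / 49.8 | 75.4 / 77.6 | 89.1 / 94.7 |

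With no gap the two rules coincide. With any gap the SAP rule is never higher. The timing of the largest error depends on the scenario: early lapse with an 8-week gap is worst at Week 12 (3.6 points, against 2.8 at Week 26 and 0.6 at Week 52), while long gaps are worst late.

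**Step 3: allow site visits to recover closures.** Assume a closure hazard of 6% per week, so true closure is 1 - exp(-0.72) = 51% at Week 12 and 1 - exp(-1.56) = 79% at Week 26. Between 10% and 30% lapse in Weeks 1-20, with a mean gap to exit of 6-26 weeks. Cells show how far the SAP rule is too low.

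| Later closures reaching the EDC | Week 12 | Week 26 |
|---|---|---|
| None | 0.5-3.2 points | 0.9-8.0 points |
| Those dated at the Week 12 and Month 12 visits | 0.1-0.9 | 0.6-4.0 |
| Those, plus half of the remainder | at most 0.4 | 0.3-2.0 |

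Censoring at last documented open was unbiased in the first two rows.

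**Step 4: test the remedy.** If the site learns of closures by telephone but accepts open status only from a visit or image, non-closers are cut early while closers keep their events. Censoring at last open then overstates Week 26 closure by up to 1.7 points. The sources for open and closed status must therefore match.

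**The case against.** The plan provides more observation than the censoring sentence suggests. Patients unhealed at Week 12 are asked to keep photographing weekly until closure (Protocol 7.1.3, 8.1.4), and the investigator can see the images (8.2.7). The 6-month call requests a photograph (8.1.7). A patient found open at the Month 12 clinic visit is censored on a date when the wound was assessed. The closure date is the site's entry in the EDC (SAP 4.3), so a closure during a photograph lapse can still be picked up at the next visit. A lost patient is dated at last contact, which may be close to the last report on the wound. The registry is single-arm and descriptive, and with 200 patients one standard error is √(0.51 × 0.49 / 200) = 3.5 points at 51% and √(0.79 × 0.21 / 200) = 2.9 points at 79%.

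All of this stands, and it limits the size. It does not repair the rule, because none of it makes the censoring date a date of wound assessment, and the bias does not shrink as patients are added.

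A reader might infer more than the documents support:

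- **That the curve is wrong as planned.** This needs patients with a gap, and the documents give neither their number nor the gap's length.
- **That the error is greatest after Week 12.** The sparse site schedule makes this plausible, but Step 2 shows that it is not general.
- **That deaths make a competing-risk analysis necessary.** The size of that effect rests on a mortality rate the documents do not give. It runs in the opposite direction and is a separate question.

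**Conclusion.** The point holds as a conditional bias. The last date on study is undefined, can be later than the last documented open status, and is not corrected elsewhere in either document. Where assessments lapse while the patient stays on study, the Kaplan-Meier curve and quartiles move toward later or lower closure, and the Cox models inherit the same times.

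With 10-30% lapsing and mean gaps of 6-26 weeks, the shortfall is about 0.1-3 points at Week 12 and 0.6-8 points at Week 26. The low ends apply if the Week 12 and Month 12 visits recover closures, and the high ends if nothing after the lapse is recorded. It is smaller still if the site learns of other closures, and zero with no gap. These figures rest on an assumed constant hazard of 6% per week and on lapse unrelated to healing. At the upper end the bias exceeds one standard error for 200 patients on a primary endpoint, which justifies a cheap change.

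**What to change.** In SAP 3.5.1.3, censor unclosed wounds at the last date the target wound was documented open, using any source that could also have recorded closure: a site visit, an evaluable image, or a contact that recorded wound status. Report the present rule as a sensitivity analysis, with last date on study defined explicitly (exit, death or last contact). Tabulate the gap between last documented open status and last date on study, so that readers can see how much the choice matters. Check SAP 3.5.2.6, which censors time to recurrence by a similar rule.

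The cost is a few SAP sentences, slightly fewer weeks at risk and slightly wider intervals. The new rule assumes that stopping assessment is unrelated to healing, and this should be stated with the results.

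An item on first closure at the 6-month call would also help, but it is a protocol amendment needing IRB/REB approval (Protocol 12.7) and may come too late for patients already past that call. The SAP change does not depend on it.

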3.5.2.3 Change in pain on NPRS compared to baseline

An 11-point NPRS is used to assess patient's level of pain. A patient is asked "What was your pain level at the ulcer location over the last 24 hours?" and selects a score between 0 and 10, with 0 meaning no pain and 10 meaning the worst pain.

Summary statistics for each visit time point and change from baseline for NPRS through 12 weeks, 6 months and 12 months post-treatment will be presented with 95% CI. NPRS

assessments from both the EDC and sDCT will be combined and slotted into windows found in section 3.1. If a patient has more than one assessment during a timepoint, the worst (highest) NPRS score will be used.

Additionally, NPRS assessments will be summarized using shift tables by each visit and worst value post baseline.

3.5.2.4 Change on EQ-5D-5L quality of life assessment compared to baseline at 12 weeks and 12 months post-treatment

The EQ-5D-5L is a self-administered questionnaire consisting of 5 questions pertaining to specific health dimensions (mobility, self-care, pain, usually activities and anxiety and depression), and health status rating scale (visual analogue scale [VAS]). Each dimension has 5 levels: no problems, slight problems, moderate problems, severe problems, and extreme problems. If a patient has died, the last EQ-5D-5L dimension assessment prior to death will be imputed as extreme problems (coded as 5).

The VAS records the respondent's self-rated health on a 20 cm vertical, visual analogue scale with endpoints labeled 'the best health you can imagine' (Score=100) and 'the worst health you can imagine' (Score = 0). This information can be used as a quantitative measure of health as judged by the individual respondents. If a patient has died, the last EQ-5D-5L VAS assessment prior to death will be imputed as 0.

Each one digit number expressing the level selected for each dimension can be combined into a 5-digit number describing the respondent's health state. For example, the number 11111 represents the respondent not having any problems in all five dimensions. These 5-digit numbers are health states which can be converted to an index value, where 1 represents full health and 0 is equivalent to death. A health state could be considered worse than death and the index values for those states will be less than 0. The index value will be calculated as:

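### If patients die with an open wound, censoring them in the time-to-closure Kaplan-Meier analysis overstates the closure probability, modestly and mainly late in follow-up

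*SAP*

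**What the plan says.** Time to closure is one of three primary endpoints (SAP 1.3: "Time from initial treatment with Varithena® to wound closure"). SAP 3.5.1.3 states that "the distribution of the time to wound closure will be analyzed by KM methodology", that "Any wound that was not closed will be censored at the last date on study", that "The 25th percentile, median and the 75th percentile will be presented along with the 95% CIs", and that "KM rates will be presented for each week with the corresponding 95% CIs". No last week is set for these rates, and a plot of the curve is also planned.

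The SAP does not define the censoring date any further. The nearest definition is the duration-on-study formula in SAP 3.3.1, which ends a patient's time at the "earlier date of study exit/death". On that reading, a patient who dies with an open wound is censored on the date of death.

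Deaths are foreseen. SAP 3.3.1 lists death among the reasons for discontinuation, and SAP 3.5.2.4 has a rule for the quality-of-life scale: "If a patient has died, the last EQ-5D-5L VAS assessment prior to death will be imputed as 0". There is no corresponding rule for closure. SAP 3.5.1.4 only rules out imputation, and protocol sections 10.1 and 10.3 name Kaplan-Meier alone.

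For time to recurrence, SAP 3.5.2.6 says that if a healed wound has not recurred, "the patient will be censored at the last date of study", again without mention of death.

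**The concern.** Kaplan-Meier treats a censored patient as one who would have gone on to close at the same rate as those still under observation. That can be reasonable for a living patient whose follow-up ends. It cannot be true of a patient who has died, because death rules out closure and is therefore a competing event. With deaths censored, one minus Kaplan-Meier describes closure in a setting where nobody dies, which is higher than the share of treated patients whose wounds close.

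The registry has one arm, so no comparator offsets the shift. A reader is likely to take the weekly rates and the curve as the proportion healed by each week. The bias goes one way, does not shrink as more patients are enrolled, and is not reflected in the planned confidence intervals.

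**Working it through.** The documents state no closure probability, quartile or death rate for this registry, so there is no figure of the plan's own to reproduce. The check compares the two estimators under stated scenarios.

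**Inputs from the documents.** Follow-up is 12 months, taken as T = 52 weeks. The planned size is about 200 patients. Three closure rates come from the background studies in protocol 4.1:
- A: 69% healed in the radiofrequency ablation series, taken as at 26 weeks (the source says at least 6 months).
- B: 62% at 12 weeks in the control group of the small foam trial.
- C: 84.8% at 21 weeks in the polidocanol foam group of a comparison with compression.

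**Assumed inputs.** Two slower scenarios: D, 75% closed at 52 weeks, and E, 50% closed at 52 weeks. Mortality over 12 months: 1%, 2%, 5% and 10%. Hazards are constant.

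**Formulas.** With p closed at week t and 12-month mortality m:
- closure hazard h = -ln(1 - p)/t; death hazard d = -ln(1 - m)/52
- one minus Kaplan-Meier, deaths censored: 1 - exp(-hT)
- cumulative incidence, death competing: [h/(h + d)] x [1 - exp(-(h + d)T)]
- time at which the cumulative incidence reaches q: -ln[1 - q(h + d)/h]/(h + d)

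**Worked case, D with 5% mortality.** h = ln(4)/52 = 0.02666 and d = 0.000986. One minus Kaplan-Meier is 1 - 0.25 = 75.0%. Since exp(-(h + d) x 52) = 0.25 x 0.95 = 0.2375, the cumulative incidence is 0.9643 x 0.7625 = 73.5%. The overstatement is 1.5 points.

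**Week 52, all scenarios.**

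| Scenario | 1 - KM | Cumulative incidence at 1 / 2 / 5 / 10% mortality | 75th percentile: KM, then 5% and 10% |
|---|---|---|---|
| A | 90.4% | 90.1 / 89.8 / 88.9 / 87.4% | 30.8, 31.6, 32.5 weeks |
| B | 98.5% | 98.3 / 98.0 / 97.4 / 96.2% | 17.2, 17.4, 17.7 weeks |
| C | 99.1% | 98.9 / 98.6 / 98.0 / 97.0% | 15.5, 15.7, 15.9 weeks |
| D | 75.0% | 74.7 / 74.4 / 73.5 / 72.0% | 52.0, then not reached by week 52 |
| E | 50.0% | 49.8 / 49.6 / 48.9 / 47.7% | not reached by any method |

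The overstatement is 0.2-0.3, 0.4-0.6, 1.0-1.5 and 2.1-3.0 points at the four mortality levels. A closure median of 20 weeks gives the largest gap under constant hazards: at 10% mortality, 83.5% against 80.5%, or 3.1 points before rounding the two percentages. At 5% mortality these scenarios imply about 2 to 7 open-wound deaths among 200 patients.

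**Week 12 and the median.** The largest week-12 difference is 0.66 point (C, 10% mortality). In A to C the median moves by at most 0.3 week. In D it moves from 26.0 to 26.4 weeks at 5% and 26.9 at 10%. In E the Kaplan-Meier median falls exactly at week 52, so any death rate above zero moves it beyond follow-up.

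**Unequal healing.** Assume 70% of wounds have a closure median of 10 weeks and 30% a median of 52 weeks. With the same death hazard in both groups, the week-52 gap is 1.2 points at 5% mortality and 2.4 at 10%. If slow healers die at twice the rate, it is 1.7 and 3.5 points. The 75th percentile moves by 0.5 to 4.3 weeks across this mixture at 2% to 10% mortality.

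**Scale.** The standard error of a 75% proportion with 200 patients is sqrt(0.75 x 0.25/200) = 3.1 points.

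**The case against.** The strongest reply is that the effect may not matter. It is zero without open-wound deaths, and no death rate is given for this registry. At 5% mortality or less it is about 1.5 points or under with constant hazards, roughly half the standard error at 200 patients. The protocol specifies Kaplan-Meier for a descriptive registry with no hypothesis test, so no decision depends on a shift of this size. The SAP speaks of the distribution of time to closure and does not call the curve the share of treated patients healed. All of this stands, and it limits the point to a conditional one. What it does not remove is the direction: sampling error is random and shown in the interval, while this bias is neither.

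Four stronger readings are tempting, and the documents do not support them:
- A reader might infer that the results will certainly be too favourable. That needs open-wound deaths, which are possible but not quantified.
- A reader might take scenario D as typical, with a 75th percentile printed at 52 weeks that is never reached. It is a knife-edge: a 26-week median puts Kaplan-Meier at exactly 75% at week 52. With the protocol's background closure rates (A to C), the 75th percentile moves by at most 0.8 week at up to 5% mortality.
- A reader might see a contradiction with SAP 3.5.1.2, where an early death would count as not closed. That section states neither a denominator nor a rule for deaths, so this is an inference.
- A reader might treat 12-month closure as a named output. It follows only from weekly rates without a cut-off and from the plot; the closure time point named as an endpoint is Week 12.

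Nor does the recurrence analysis flatter the product. There Kaplan-Meier overstates recurrence, and the weekly rates stop at 12 weeks, so any effect lies mainly in later quartiles and the plot.

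**Conclusion.** The point holds in conditional form. The censoring rule in SAP 3.5.1.3 covers deaths and nothing else in either document corrects it. If patients die with an open wound and closures follow, one minus Kaplan-Meier exceeds the probability that a treated patient's wound closes, and the 75th percentile may come out too early. The week-52 overstatement rises from about 0.2-0.3 point at 1% mortality to about 2.1-3.1 points at 10%, and somewhat more if slow healers also die sooner. These sizes rest on assumed mortality and assumed hazard shapes.

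The Week 12 closure proportion is untouched by this rule. The median is essentially unaffected unless closure at 12 months is close to 50%. This is a cheap improvement to a primary analysis, not a defect that undermines it.

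**What to change.** In SAP 3.5.1.3, report the number of patients who die with an open wound. Add the weekly cumulative incidence of closure by the Aalen-Johansen estimator, with death before closure as a competing event and 95% confidence intervals, and give the quartiles from that curve. Keep the Kaplan-Meier display specified in the protocol alongside, and record the addition in SAP section 2.

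State explicitly that a patient who dies leaves the risk set on the date of death. The Cox models in SAP 3.6 can stay, read as cause-specific models for closure. The same display can be added in SAP 3.5.2.6 with death before recurrence as the competing event.

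The cost is some SAP wording, a standard procedure option and one more set of outputs. Death dates are already needed for duration on study, so no new data or visits are required. The closure percentages will be slightly lower than under Kaplan-Meier if open-wound deaths occur.
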